The lungs are known to be colonised with different strains of bacteria [[Erb-Downward](#), 2011]. In COPD patients, acquisition of new bacterial strains is believed to be an important cause of AECOPD [[Sethi](#), 2002]. Although estimates vary widely, Non-typeable *Haemophilus influenzae* (NTHi) appears to be the main bacterial pathogen associated with AECOPD (11-38%), followed by *Moraxella catarrhalis* (*M. catarrhalis*) (3-25%) and *Streptococcus pneumoniae* (*S. pneumoniae*) (4-9%) [[Alamoudi](#), 2007; [Bandi](#), 2003; [Hutchinson](#), 2007; [Ko](#), 2007; [Larsen](#), 2009; [Murphy](#), 2005; [Papi](#), 2006; [Sethi](#), 2002; [Sethi](#), 2008].

Reducing the frequency and severity of AECOPD is one of the main goals of COPD maintenance treatment. The severity of AECOPD can be graded according to the intensity of medical intervention required (see [Table 2](#)) [[Wedzicha, 2007](#)].

Table 2 Classification of severity of AECOPD

Grade	Intensity of medical intervention
Mild	Can be controlled with an increase in dosage of regular medications
Moderate	Requires treatment with systemic corticosteroids and/ or antibiotics
Severe	Requires hospitalisation

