5.2. Inclusion criteria for enrolment

Deviations from inclusion criteria are not allowed because they can potentially jeopardise the scientific integrity of the study, regulatory acceptability or subject safety. Therefore, adherence to the criteria as specified in the protocol is essential.

All subjects must satisfy ALL the following criteria at study entry:

- Subjects who, in the opinion of the investigator, can and will comply with the requirements of the protocol (*e.g.* electronic Diary Card completion, number of blood draws, sputum sampling, pre- and post-bronchodilator spirometry, return for follow-up visits).
- A male or female between, and including, 40 and 80 years of age at the time of the first vaccination.
- Written informed consent obtained from the subject.

- Confirmed diagnosis of COPD (based on post-bronchodilator spirometry) with forced expiratory volume in 1 second (FEV₁) over forced vital capacity (FVC) ratio (FEV₁/FVC) < 0.7, **AND** FEV₁ < 80% and ≥ 30% predicted (GOLD 2 and 3).

- Current or former smoker with a cigarette smoking history of ≥ 10 pack-years.
Refer to the [glossary of terms](#) for the definitions of pack-years and of current and former smoker.

- Stable COPD patient* with documented history (e.g. medical record verification) of at least 1 moderate or severe AECOPD within the 12 months before Screening.

* Patient for whom the last episode of AECOPD is resolved for at least 30 days at the time of Screening.

Refer to the Study Procedures Manual (SPM) for details on what is accepted as documented history of AECOPD. Refer to [Table 2](#) for the definitions of moderate and severe AECOPD.

- Regular sputum producer.
- Capable to comply with the daily electronic Diary Card completion throughout the study period, according to investigator's judgement at Visit 1.

Refer to the SPM for recommendations on what is considered adequate compliance by Visit 1.

- Female subjects of non-childbearing potential may be enrolled in the study.
 - Non-childbearing potential is defined as current tubal ligation, hysterectomy, ovariectomy or post-menopause.
Refer to the [glossary of terms](#) for the definition of menopause.
- Female subjects of childbearing potential may be enrolled in the study, if the subject:
 - has practiced adequate contraception for 30 days prior to vaccination, and
 - has a negative pregnancy test on the day of vaccination, and

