6.2.2.2. Treatment allocation to the subject

The treatment numbers will be allocated by dose.

6.2.2.2.1. *Study group and treatment number allocation*

The target will be to enrol approximately 140 eligible subjects who will be randomly assigned to the 2 study groups in a (1:1) ratio (approximately 70 subjects in each group).

Allocation of a subject to a study group at the investigator site will be performed using a centralised randomisation system on the internet (SBIR). The randomisation algorithm will use a minimisation procedure accounting for age (40 - 59 years or 60 - 80 years), number of moderate/ severe AECOPD in the previous year (< 2 or \geq 2) and GOLD grade (GOLD 2 or GOLD 3). All factors will have equal weight in the minimisation algorithm.

At Visit 1, before administration of vaccine Dose 1 to eligible subjects who signed and dated the ICF at the Screening Visit, the dedicated site staff will access SBIR. Upon providing the subject's age category (40 - 59 years or 60 - 80 years), number of moderate/ severe AECOPD in the previous year and his/ her GOLD grade, the randomisation system will determine the study group and will provide the treatment number to be used for the first dose.

The number of each administered treatment must be recorded in the eCRF on the Vaccine Administration screen.

When SBIR is not available, refer to the SBIR user guide or the SPM for specific instructions.

6.2.2.2.2. *Treatment number allocation for subsequent doses*

For each dose subsequent to the first dose, the dedicated study staff will access SBIR. Upon providing the subject identification number, the system will provide a treatment number consistent with the allocated study group.

The number of each administered treatment must be recorded in the eCRF on the Vaccine Administration screen.

When SBIR is not available, refer to the SBIR user guide or the SPM for specific instructions.

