6.1.3. Analysis of impact of the investigational vaccine on AECOPD incidence

The analysis will be performed on the ATP cohort for efficacy. If the percentage of vaccinated subjects excluded from the ATP cohort for efficacy is more than 10%, a second analysis based on the TVC will be performed to complement the first analysis.

The following incidence rates will be computed over a period starting 1 month post-Dose 2 and lasting for 1 year, with 95%CI:

- NTHi-associated moderate and severe AECOPD. (See definition in section 7.1.4)
- NTHi-associated all-severity AECOPD.
- All-cause moderate and severe AECOPD.
- All-cause, all-severity AECOPD.

Vaccine efficacy (VE) for AECOPD events will be defined as:

$$VE (AECOPD) = 1 - R_{vaccine} / R_{control}$$

with:

- $R_{vaccine}$ = average yearly incidence rate of AECOPD events per subject in the group 10-AS01E.
- $R_{control}$ = average yearly incidence rate of AECOPD events per subject in the Control group.

In case the 95% CI of the VE cannot be estimated, *e.g.* when no event is observed in the group 10-AS01E (leading to a VE of 100%), then an exact procedure will be used to estimate a VE and its 95% CI. This exact procedure will be based on the number of subjects with event instead of on the average number of event per subject in each group.

Statistical Analysis Plan

Study alias & e-track number(s): NTHi-004 (200157)

VE in the prevention of NTHi-associated moderate and severe AECOPD and its 95% CI will be calculated.

VE in the prevention of NTHi-associated all-severity AECOPD, of all-cause moderate and severe AECOPD and of all-cause, all-severity AECOPD and their 95% CI will also be calculated.

The 95%CI of the incidence rate will be computed using a model which accounts for repeated events. The Generalised linear model assuming the Negative Binomial distribution for the response variable with logarithm as link function, and the logarithm of time for follow-up as an offset variable will be used. In addition, the following covariates (as per randomization) will be taken into account:

- country,
- number of moderate/severe exacerbations reported in the 12 months prior to enrolment,
- COPD status at enrolment (derived by GSK from the Visit 1 spirometry results)
- Age (below or equal to median/above median)

If the model does not converge, the Poisson distribution will be used instead of the Negative Binomial one.

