7.1.3. Immunogenicity

- For a given subject and the analysis of a given immunogenicity measurement, missing or un-evaluable measurements will not be replaced.
- A seronegative subject is defined as a subject whose antibody concentration is below the assay cut-off value.
- A seropositive subject is defined as a subject whose antibody concentration is greater than or equal to the assay cut-off value.
- Antibody concentrations below the assay cut-off will be given an arbitrary value of half the assay cut-off for the purpose of geometric mean concentration (GMC) calculation.
- Calculation of the GMCs will be performed by taking the anti-logarithm in base 10 (anti-log10) of the mean of the log10 concentration transformations.

Statistical Analysis Plan

Study alias & e-track number(s): NTHi-004 (200157)

- The assay cut-off is the value under which there is no quantifiable result for which no accuracy and precision can be reported. For an assay with a specific 'cut_off' , numerical immuno result is derived from a character field (rawres):
 - If rawres is 'NEG' or '-' or '(-)', numeric result= cutt_off/2,
 - if rawres is 'POS' or '+' or '(+)', numeric result = cut_off,
 - if rawres is '< value' and value<=cut_off, numeric result =cut_off/2,
 - if rawres is '< value' and value>cut_off, numeric result =value,
 - if rawres is '> value' and value<cut_off, numeric result =cut_off/2,
 - if rawres is '> value' and value>=cut_off, numeric result =value,
 - if rawres is '<= value' or '>= value' and value<cut_off, numeric result =cut_off/2,
 - if rawres is '<= value' or '>= value' and value>=cut_off, numeric result =value,
 - if rawres is a value < cut_off, numeric result = cut_off/2,
 - if rawres is a value >= cut_off, numeric result = rawres,
 - else numeric result is left blank.
- All CI computed will be two-sided 95% CI.

Impact of the investigational vaccine on AECOPD

- For a given subject and the analysis of a given laboratory assay, missing or un-evaluatable measurements will not be replaced.
- Subjects who did not have any sputum collected during at least 1 AECOPD (if at least 1 AECOPD occurred) will not be taken into account for the NTHI-associated AECOPD analyses.

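### The Poisson fallback for AECOPD rates carries no variance correction, so the intervals are moderately too narrow if the negative binomial fails while counts are overdispersed

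*SAP*

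**What the plan says.** SAP Amendment 1 section 6.1.3 gives the purpose of the model first: "The 95%CI of the incidence rate will be computed using a model which accounts for repeated events". It then names it: "The Generalised linear model assuming the Negative Binomial distribution for the response variable with logarithm as link function", with log follow-up time as offset. The covariates are country, prior moderate or severe exacerbations, COPD status at enrolment, and age split at the median. The last step is the fallback: "If the model does not converge, the Poisson distribution will be used instead of the Negative Binomial one". Protocol section 11.10 has the same model and fallback, without the covariate list.

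Neither document names a scale parameter, a robust variance, a check for overdispersion, or a remedy to try before changing model. Section 6.1.3 has one other fallback: if the VE interval cannot be estimated, for example with no events in the vaccine group, an exact method based on subjects with an event is used.

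The rule covers four rates, NTHi-associated and all-cause, each for moderate and severe events and for all severities, "over a period starting 1 month post-Dose 2 and lasting for 1 year, with 95%CI". SAP section 8.1 also has AECOPD analysed at the interim data lock, when there will be fewer events.

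**The concern.** A Poisson model sets the variance of a subject's count equal to its mean. The negative binomial adds a term for differences in underlying rate between subjects, which is how it meets the stated aim of allowing for repeated events. The fallback removes that term and puts nothing in its place.

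The trigger is also not a test of what matters. A negative binomial fit can stop because the data show no extra variation, and then Poisson is a reasonable replacement. It can also stop because events are few relative to the covariates, and then extra variation may still be present. The plan treats both alike. The exact method does not rescue the second case: with events in both groups, Poisson returns an interval, so the condition for the exact method is not met.

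At stake is the width of the intervals around the incidence rates and the exploratory VE.

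**Working it through.** **Inputs from the documents**
- Group size: "randomly assigned to the 2 study groups in a (1:1) ratio (approximately 70 subjects in each group") (protocol section 6.2.2.2).
- Follow-up: 1 year from 1 month after Dose 2.
- Confidence level: "All CI computed will be two-sided 95% CI" (SAP section 7.1.3).
- Entry criterion: "at least 1 moderate or severe AECOPD within the 12 months before Screening" (protocol section 5.2).
- NTHi share: it "appears to be the main bacterial pathogen associated with AECOPD (11-38"%) (protocol section 1.1.1).

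**Assumptions.** The documents give no AECOPD rate, dispersion k or effect size. Rates of 0.2 to 1.5 per year and k of 0 to 2 are used. At 1 AECOPD per year, the NTHi share implies 0.11 to 0.38 NTHi events per year, or 70 x 0.11 = 7.7 to 70 x 0.38 = 26.6 events per group. So 0.2 to 0.3 per year is a plausible range for the NTHi endpoints.

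**The plan's own figure.** The only sample-size figures concern detecting an adverse event with 70 subjects (protocol section 11.4). 1 - 0.99^70 = 50.5% and 1 - 0.95^70 = 97.2%, so both stated figures reproduce. They do not bear on the AECOPD model.

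**Step 1: coverage if plain Poisson were used in every trial.** For the log rate ratio with n = 70 per group, equal rates m and full follow-up:
- Poisson variance = 2/(nm)
- True variance = 2/(nm) + 2k/n
- Coverage = 2 x Phi(1.96 x SE_Poisson / SE_true) - 1

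| Rate/yr | k | Poisson SE | True SE | Coverage |
|---|---|---|---|---|
| 0.2 | 1 | 0.378 | 0.414 | 92.6% |
| 0.2 | 2 | 0.378 | 0.447 | 90.2% |
| 0.3 | 1 | 0.309 | 0.352 | 91.4% |
| 0.3 | 2 | 0.309 | 0.390 | 87.9% |
| 1.0 | 0.5 | 0.169 | 0.207 | 89.0% |
| 1.0 | 1 | 0.169 | 0.239 | 83.4% |
| 1.5 | 1 | 0.138 | 0.218 | 78.5% |

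Simulation without covariates (2,000 trials per scenario) agrees: 89.8% at 1 per year with k = 0.5, and 82.5% with k = 1. With k = 0, Poisson covers 95 to 96%.

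**Step 2: how often the fallback would be reached.** What counts as non-convergence depends on the software, so a dispersion estimate of zero is taken as a proxy. Without covariates it occurred in:
- 57 to 60% of trials at k = 0
- 47% at 0.2 per year, k = 0.25
- 8% at 0.5 per year, k = 0.5
- at most 0.2% at 1 per year or more, k of 0.5 or more

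With covariates (assumed: four countries of uneven size and three binary factors) it was 1.0% at 1 per year with k = 0.5, and at most 0.1% at 1 per year with k of 1 or more. The lower rows of the table therefore describe trials in which this trigger seldom arises.

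**Step 3: coverage given the reason for failure.**
- Dispersion estimate at zero: where at least 35 trials had such an estimate, plain Poisson covered 93 to 96%, falling to 90% at 0.2 per year with k = 2.
- Negative binomial failed with visible overdispersion (same assumed covariate structure, 0.2 to 0.3 per year, k = 1 to 2): plain Poisson covered about 87 to 91%, robust Poisson about 92 to 93%, Pearson-scaled Poisson 94 to 95%.

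**Step 4: effect on a VE interval.** Take VE 30%, control rate 0.2 per year and k = 2. Poisson variance = 1/14 + 1/9.8 = 0.173, SE 0.416, interval -58% to 69%. Adding 2 x 2/70 = 0.057 gives SE 0.480, interval -79% to 73%.

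**The case against.** The best case against is that large undercoverage and likely use of the fallback mostly do not coincide. Where rates are high enough for the shortfall to be large, the overdispersion is visible and the negative binomial can normally be fitted. Where events are rare, the shortfall is a few points, and the typical failure is a zero dispersion estimate, for which Poisson is nearly right. This stands, and it limits the size of the point.

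A country with no events sends its coefficient to infinity in the Poisson model as well, so that problem is not specific to the negative binomial. This also stands. It narrows the damaging case but does not remove it, because Step 3 shows failures with visible overdispersion and a real shortfall.

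A third objection is that a variance correction does little when the dispersion estimate is zero. In such trials at 0.2 per year (k = 0.5) and 0.3 per year (k = 1), plain Poisson covered 94.1% and 94.9%, Pearson scaling 94.1% and 94.2%, and robust errors 92.9% and 93.1%. That is true, and it favours Pearson scaling over robust errors. With the scale held at 1 or more, the interval can never be narrower than plain Poisson.

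A reader might infer that coverage of 83 to 89% is to be expected for the all-cause rates. The documents do not support that: those figures assume Poisson is always used, whereas the plan uses it only on non-convergence. A reader might also infer an inflated confirmatory error rate. Protocol section 11.3 makes the AECOPD counts tertiary, section 11.13 makes the group comparisons descriptive, and no decision rule uses these intervals.

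**Conclusion.** The point holds in a limited form. The fallback drops the protection for which the negative binomial was chosen, on a trigger that does not show the protection is unnecessary. Where the fit fails at zero dispersion, little is lost. Where it fails with overdispersion present, a nominal 95% interval covers about 87 to 91% at the assumed 0.2 to 0.3 events per year and k of 1 to 2. How often that second case would occur is not established.

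The consequence is overstated precision of exploratory rate and VE intervals. The event rates, k, the country layout and complete follow-up are all assumptions, since the documents give no planning values for AECOPD.

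**What to change.** Replace the fallback sentence in SAP section 6.1.3, and align protocol section 11.10. State that if the negative binomial model does not converge, a Poisson model with the same terms will be fitted, with standard errors multiplied by the square root of the Pearson chi-square divided by its residual degrees of freedom, that ratio being set to 1 if it is lower. Report for each endpoint, and for the interim and final analyses separately, which model produced the interval.

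Robust standard errors would also be an improvement, but covered slightly less well than Pearson scaling in the case that matters. Whether to simplify the country term before falling back is a matter of preference and is not part of this change.

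The cost is one SAP sentence, one procedure option and one table footnote. The only statistical downside is a slightly wider interval when counts are not overdispersed.

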3.3. Tertiary objectives

- To explore the impact of the investigational vaccine on AECOPD.
- To explore the impact of the investigational vaccine on NTHi presence in sputum.
- To explore the impact of the investigational vaccine on health-related quality of life (HRQOL).
- To explore the impact of the investigational vaccine on lung function.
- To explore the impact of the investigational NTHi vaccine on exercise capacity.
- To describe selected biomarkers in stable COPD and during AECOPD.
- To collect blood and sputum samples for assay development, for disease diagnostic purpose, for lung microbiome analysis and/ or for additional evaluation of the immune responses to the investigational vaccine and to other potential pathogens involved in AECOPD.

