4.3. Tertiary endpoints

- Number of cases of NTHi-associated moderate and severe AECOPD, over a period starting 1 month post-Dose 2 and lasting for 1 year, in all subjects.
- Number of cases of NTHi-associated AECOPD (any severity), over a period starting 1 month post-Dose 2 and lasting for 1 year, in all subjects.
- Number of cases of moderate and severe AECOPD (any cause), over a period starting 1 month post-Dose 2 and lasting for 1 year, in all subjects.
- Number of cases of AECOPD (any cause, any severity), over a period starting 1 month post-Dose 2 and lasting for 1 year, in all subjects.
- Time to first AECOPD, in all subjects.
- Assessment of EXACT-PRO score, daily at bedtime throughout the study, in all subjects.
- NTHi presence in sputum, at Screening, Day 90, Day 180, Day 270, Day 360 and Day 450, and from first vaccination to study conclusion for each AECOPD, in all subjects.
- Assessment of CAT score, at Screening, Day 270 and Day 450, and from first vaccination to study conclusion for each AECOPD, in all subjects.
- Assessment of SGRQ-C score, at Screening, Day 270 and Day 450, in all subjects.
- Assessment of mMRC scale, at Screening, Day 270 and Day 450, and from first vaccination to study conclusion for each AECOPD, in all subjects.
- Occurrence of rescue medication use, over a period starting 1 month post-Dose 2 and lasting for 1 year, in all subjects.
- Occurrence of healthcare use for AECOPD, over a period starting 1 month post-Dose 2 and lasting for 1 year, in all subjects.

Statistical Analysis Plan

Study alias & e-track number(s): NTHi-004 (200157)

- Assessment of FEV1% of predicted normal value at Screening, Day 270 and Day 450, in all subjects.
- Assessment of 6MWT score, at Screening and Day 450, in all subjects.
- Occurrence of selected biomarkers in a subset of blood samples, at Day 0 and Day 450, and from first vaccination to study conclusion for each AECOPD, in all subjects.
- Presence of respiratory viral pathogens in sputum (including respiratory syncytial virus, parainfluenza virus, enterovirus/ rhinovirus, metapneumovirus, influenza virus, adenovirus, bocavirus and coronavirus) at Screening, Day 90, Day 180, Day 270, Visit Day 360 and Day 450 and at each AECOPD visit from first vaccination to study conclusion, in all subjects.

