6.1.2. Analysis of immunogenicity

The analysis will be performed on the ATP cohort for immunogenicity. If the percentage of vaccinated subjects with serological results excluded from the ATP cohort for analysis of immunogenicity is more than 10%, a second analysis will be performed on the TVC.

Humoral immune response

Within group evaluation

For each group, at each time point during which blood samples are collected for humoral immune response and for each assay:

- Seropositivity rate and their exact 95% CI will be tabulated.
- GMCs and their 95% CI will be calculated.

For each group, at each time point during which blood samples are collected for humoral immune response:

- Antibody concentrations distribution will be investigated using Reverse Cumulative Curves.

Between groups evaluation

Comparative analyses will be exploratory with the aim to characterise the difference between the 2 groups in humoral immune response.

The difference in terms of GMCs will be evaluated at 1 month post-Dose 2 and at Day 450 by computing the 95% CIs of the GMC ratio between groups by using an ANCOVA model that considers heterogeneity of variances (via Proc Mixed) on the logarithm10 transformation of the concentrations. This model will include the country, the group, age category (40 - 59 years or 60 - 80 years), number of moderate and severe AECOPD in the year before vaccine Dose 1 (< 2 or \geq 2), GOLD grade (GOLD 2 or GOLD 3) and pre-Dose 1 concentration (as covariate) as fixed effects.

Statistical Analysis Plan

Study alias & e-track number(s): NTHi-004 (200157)

However, these differences should be interpreted with caution considering that there will be no adjustment for multiplicity of endpoints.

Cell-mediated immune response

The frequency of specific CD4⁺/ CD8⁺ T-cells will be summarised (mean, SD, minimum, Q1, median, Q3, and maximum) by group, at each time point during which blood samples are collected for CMI (descriptive statistics).

Each data will be obtained by subtracting the summary of the background value to each summary value. Values less than or equal to zero will be set to 1 for the purpose of geometric mean calculation and graphical representation.

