The frequency of all these AECOPDs will be presented. The estimated incidence rate with 95%CI of AECOPDs in which Hi (resp. Mcat, Sp) is present in culture and was not present in the previous visit estimated by a Generalised linear model assuming the Negative Binomial distribution will be estimated.

Time to first AECOPD event by baseline status - Cox regression model

The Cox's regression model including the risk factors:

- country,
- number of moderate/severe exacerbations reported in the 12 months prior to enrolment,
- COPD status at enrolment (derived by GSK from the Visit 1 spirometry results)
- Age (below or equal to median/above median)

as covariates (as per randomization) will be performed to model the time until the first occurrence of AECOPD episodes. Additional stratification/risk factor may be defined during the analyses like sex factor as exploratory analysis.

Statistical Analysis Plan

Study alias & e-track number(s): NTHi-004 (200157)

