6.1.4. AECOPD visits and daily questionnaires

The time until first AECOPD as of 1 month post-Dose 2 will be computed with exact 95% CI by group. Subjects who exacerbate before 1 month post-Dose 2 will not be taken into account in this analysis.

The number of morning e-dairy (PHT) alerts (resp. evening e-diary alerts (EXACT-PRO)) with and without corresponding site visits will be tabulated. The reason for inconsistency between morning e-diaries and site visits will also be presented.

The number of exacerbation site visits with confirmed AECOPD with and without morning e-diary alerts (resp. evening e-diary alerts (EXACT-PRO)) will be tabulated along with the reason for no e-diary alert.

Concordance/discordance of exacerbations periods as defined clinically or via the morning diary cards or the evening diary cards will be tabulated and presented graphically.

The percentage of spontaneous exacerbation visits will be tabulated as well as the percentage of monthly visits with recovered/stable status.

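### The only regression planned for time to first AECOPD lists four baseline covariates and no study group, so as written it gives no vaccine hazard ratio

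*SAP*

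**What the plan says.** SAP Amendment 1 lists "Time to first AECOPD, in all subjects" as a tertiary endpoint (4.3). The objective it serves is "To explore the impact of the investigational vaccine on AECOPD" (3.3).

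Two analyses address it:

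- **Section 6.1.3**, the section on vaccine impact, has a paragraph headed "Time to first AECOPD event by baseline status - Cox regression model". It begins "The Cox's regression model including the risk factors" and lists country, moderate or severe exacerbations in the year before enrolment, COPD status at enrolment, and age split at the median. These enter "as covariates (as per randomization) will be performed to model the time until the first occurrence of AECOPD episodes". The one stated extension is: "Additional stratification/risk factor may be defined during the analyses like sex factor as exploratory analysis".
- **Section 6.1.4** states: "The time until first AECOPD as of 1 month post-Dose 2 will be computed with exact 95% CI by group". Subjects who exacerbate before that point are left out. Protocol 11.10 plans the same computation.

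The Cox list is the same in SAP Version 1 (6.2.4), so the amendment did not change it. The protocol has no Cox model. Neither document mentions a log-rank test or a hazard ratio.

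**The concern.** A proportional hazards model with only baseline terms pools vaccine and placebo subjects. It returns hazard ratios for the baseline factors and nothing for the vaccine. The objective asks about vaccine impact, and the model sits in the section devoted to that impact, yet its stated terms and heading describe a prognostic analysis.

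The text also leaves room for two different outputs. One programmer could fit the pooled prognostic model; another could add group and report a vaccine hazard ratio. Under SAP 8.1 the project statistician is unblinded at the Day 90 step, with AECOPD analyses run in parallel, so the choice could be made with treatment assignments known. At stake is one exploratory effect estimate from data already being collected.

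**Working it through.** **1. The plan's own design figure.** Protocol 11.4 bases the sample size on detecting an adverse event with 70 subjects per group:

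- 1 - 0.99^70 = 0.505, against the stated figure of more than 50% at 1% incidence.
- 1 - 0.95^70 = 0.972, against the stated figure of more than 97% at 5% incidence.

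Both reproduce. Neither bears on AECOPD: no event count, hazard ratio or power is given for it.

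**2. How the SAP writes its models (Amendment 1).**

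| Analysis | Group among the terms? | Output that requires group? |
|---|---|---|
| ANCOVA, 6.1.2 | Yes: "This model will include the country, the group, age category (40 - 59 years or 60 - 80 years" | Yes, the GMC ratio between groups |
| Negative binomial, 6.1.3 | Not in the covariate list | Yes, VE is 1 minus the ratio of vaccine to control rates |
| Cox, 6.1.3 | No | None stated |
| Time to first AECOPD, 6.1.4 | Not a model; computed separately by group | No contrast between groups |

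For the negative binomial model, group can be recovered from the definition of VE. The Cox paragraph names no output from which it could be recovered. The 6.1.4 result is one estimate and interval per group; it is by-group information, but not an effect estimate.

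**3. Time origin.** The incidence window in 6.1.3 and the computation in 6.1.4 both start 1 month after Dose 2. The Cox paragraph does not repeat this origin, and it does not say whether the 6.1.4 exclusion of earlier exacerbators carries over.

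**4. Precision of a hazard ratio once group is added.** Inputs:

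- 140 subjects, 1:1 allocation (protocol 6.2.2.2.1).
- Two-sided 95% intervals (SAP 7.1.3).
- *Assumed:* 40% to 70% of all 140 subjects have a first event, i.e. d = 0.40 × 140 = 56 to 0.70 × 140 = 98.

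Approximation: SE(log HR) = 2/√d; 95% CI = HR divided and multiplied by exp(1.96 × SE).

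- d = 56: SE = 2/√56 = 0.267; factor 1.69; HR 0.70 has CI 0.41 to 1.18.
- d = 98: SE = 2/√98 = 0.202; factor 1.49; HR 0.70 has CI 0.47 to 1.04.

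Widening the assumption to 30%-80% (42 to 112 events) gives SE 0.309 to 0.189 and factors 1.83 to 1.45. An observed HR of 1 would then have a CI of 0.55-1.83 to 0.69-1.45.

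**The case against.** The strongest reply is that group is implied. The Cox paragraph repeats the negative binomial model's four items and the same label tying them to randomisation, in a section about vaccine impact. The negative binomial list omits group too, and nobody doubts that group belongs there. This may well be a drafting gap. That stands as an explanation, but VE settles the matter for one model and nothing does so for the other, while the baseline-status heading points the opposite way.

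A second reply is that the model is deliberately prognostic and that 6.1.4, as the protocol planned, is the vaccine analysis. Protocol 11.13 makes comparisons descriptive, and 6.1.3 already models VE for four AECOPD definitions. This limits the consequence: the AECOPD objective is not left without modelled effect estimates. It does not supply one for time to first event. The layouts of tables and figures are in an annex that was not available for this review and might show a group contrast.

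A reader might infer three stronger things, none of which the documents support:

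- *That the endpoint has no by-group analysis.* Section 6.1.4 provides one.
- *That it has no time origin anywhere.* Sections 6.1.3 and 6.1.4 use 1 month post-Dose 2; the Cox paragraph merely fails to repeat it.
- *That omitting group distorts the risk-factor hazard ratios.* Allocation is 1:1 and minimised on age, AECOPD history and GOLD grade (protocol 6.2.2.2.1), so group should be close to independent of those factors and material confounding is not expected.

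**Conclusion.** The point holds on the text. The only regression for time to first AECOPD contains no treatment term and yields no vaccine hazard ratio as written, and no other planned output gives a between-group effect estimate for this endpoint.

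Its weight is moderate. The endpoint is tertiary, comparisons are descriptive, and VE is modelled elsewhere in the section. The change is recommended because it is nearly free and lets the analysis address its own objective.

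The precision figures are illustrative. They rest on an assumed 56 to 98 first events among all 140 subjects. The ATP efficacy cohort used in 6.1.3, and any exclusion of earlier exacerbators, would reduce the events and widen the intervals. For a hazard ratio of 0.70 the interval already includes 1 at both ends of the assumed range, so the estimate would be exploratory and could not be read as a test of efficacy.

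**What to change.** In SAP 6.1.3:

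- Add study group (10-AS01E vs Control) as a term in the Cox model.
- Report the adjusted hazard ratio with its 95% CI, labelled exploratory and descriptive.
- State that time runs from 1 month post-Dose 2, as in the incidence analysis and 6.1.4, with censoring at withdrawal or at the end of the 1-year period.
- State whether the 6.1.4 exclusion of subjects who exacerbate earlier applies to this model.

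The baseline hazard ratios remain available from the same fit. If the model is meant to be prognostic only, the SAP should say so and specify a separate between-group estimate.

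The cost is one model term and a few lines of SAP wording. No new data are needed.
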